2.4 Sample Size Determination

This is the LTE study for Study M19-130. All eligible subjects who completed Study M19-130 will be enrolled in this study if the subject signs and dates the informed consent. Based on discontinuation criteria mandating efficacy in Study M19-130, it is anticipated that between 60% and 80% of subjects from Study M19-130 (195 to 260 subjects) will be enrolled in this LTE study.

3.0 Endpoints

3.1 Primary Efficacy Endpoint

There is no primary efficacy endpoint since this is the extension to the feeder Study M19-130. The primary objective is to investigate the longer-term safety of the ABBV-599 combination in patients with active SLE.

3.2 Secondary Efficacy Endpoints

- SLE Responder Index (SRI)-4
- British Isles Lupus Assessment Group (BILAG)-Based Combined Lupus Assessment (BICLA)
- Steroid burden, assessed as change from M19-130 baseline
- Number of mild/moderate, or severe flares per patient-year (respectively and overall) by Safety of Estrogens in Lupus Erythematosus National Assessment (SELENA) SLEDAI Flare Index (SFI), assessed by number and types of flare per subject compared across treatment groups

3.3 Other Efficacy Endpoints

The secondary efficacy endpoints are listed in Section 3.2. The additional efficacy endpoints are:

- Lupus Low Disease Activity State (LLDAS)
- \geq 4-point decrease in SLEDAI-2K compared with M19-130 Baseline
- Achievement of 50% reduction of tender or swollen lupus joints (of those starting with total \geq 6 affected joints) from M19-130 Baseline
- Achievement of 50% reduction in Cutaneous Lupus Erythematosus Disease Area and Severity Index (CLASI) activity score (of those starting with CLASI \geq 10 at M19-130 Baseline)
- Change in SLEDAI-2K from M19-130 Baseline
- Change in BILAG from M19-130 Baseline
- Change in Functional Assessment of Chronic Illness Therapy - Fatigue (FACIT-F) from M19-130 Baseline
- Change in 36-Item Short Form Health Survey (SF-36) PCS and MCS from M19-130 Baseline
- Change in Lupus Quality of Life questionnaire (LupusQoL) from M19-130 Baseline
- Change in Pain Numerical Rating Scale (NRS) from M19-130 Baseline

3.4 Safety Endpoints

The following safety evaluations will be performed for the entire study duration as measures of safety and tolerability:

- AE monitoring
- Physical examinations
- Vital sign measurements
- ECGs
- Clinical laboratory testing (hematology, chemistry, and urinalysis)

3.5 Additional Endpoint(s)

No additional endpoints will be analyzed in the SAP.

4.0 Analysis Populations

The following population sets will be used for the analyses.

The Full Analysis Set (FAS) includes all subjects who completed Study M19-130 and received at least 1 dose of assigned study drug in Study M20-186. The FAS will be used for efficacy and baseline analyses. Subjects will be grouped according to treatment sequence as randomized for Study M19-130 and continued/reassigned to rollover into Study M20-186.

The Safety Analysis Set also includes all subjects who completed Study M19-130 and received at least 1 dose of assigned study drug in Study M20-186. Subjects will be grouped according to treatment sequence actually received. A subject's actual treatment will be determined by the most frequent dose regimen received. The Safety Analysis Set will be used for safety analyses.

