7.2 Definition for Analysis Populations

The Full Analysis Set (FAS) includes all subjects received at least 1 dose of study drug in LTE Study M20-186. The FAS will be used for efficacy and baseline analyses. Subjects will be grouped according to treatment sequence as randomized for Studies M19-130 and M20-186.

The Safety Analysis Set includes all subjects who received at least 1 dose of study drug in LTE Study M20-186. Subjects will be grouped according to treatment sequence actually received. The Safety Analysis Set will be used for safety analyses.

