7.4 Statistical Analyses for Safety

All safety analyses will be performed on the Safety Analysis Set.

All treatment-emergent adverse events (TEAEs), SAEs, AEs leading to discontinuation, and AESI will be collected during the study. A TEAE is defined as an event with onset or worsening after the first study dose of study drug and within 30 days after the last dose of study drug administration. The number and percentages of subjects experiencing TEAEs will be tabulated using the Medical Dictionary for Drug Regulatory Activities (MedDRA®) System Organ Class (SOC) and preferred term (PT). Summaries (including percentages and events per 100 patient-years) of SAEs, deaths, AEs leading to discontinuation, and AESI will be provided as well. For selected laboratory and vital sign parameters, mean change from Baseline and the percentage of subjects with evaluations meeting pre-defined criteria for Potentially Clinically Important values will be summarized.

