2.0 Study Design and Objectives

2.1 Objectives and Hypotheses

Primary

The primary objective is to evaluate the longer-term safety and tolerability of elsubrutinib and upadacitinib given alone or as the ABBV-599 (elsubrutinib/upadacitinib) combination in SLE subjects who have completed the M19-130 Phase 2 study.

There is no planned hypothesis to be tested for this long-term extension (LTE) study.

Secondary

[figure not shown]
The secondary objective is to obtain longer-term efficacy data beyond Week 48 with the treatments studied in the RCT (monotherapies and combination) to more fully assess the risk/benefit of each treatment over time.

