9.0 Safety Analyses

9.1 General Considerations

Safety analyses will include reporting of adverse events, laboratory, and vital signs measurements based on data in Study M20-186. Safety analyses will be carried out using the Safety Analysis Set.

The following summary statistics will be presented for subjects who have both baseline and post-baseline values for laboratory parameters and vital signs: the mean value at Baseline and at each respective protocol specified visit, and the mean, standard deviation and median for changes from Baseline. Categorical data will be summarized using frequencies and percentages. The number of non-missing values will be given. Missing safety data will not be imputed.

For safety analysis, Baseline is defined as the last available measurement before Study M19-130 study drug administration if the subjects took active treatment in Study M19-130, and the last available measurement before Study M20-186 study drug administration if the subjects took placebo in Study M19-130.

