Appendix A. Protocol Deviations

The number and percentage of subjects who reported at least one of the following protocol deviation categories will be provided.

- Subject entered into the study even though s/he did not satisfy entry criteria.
- Subject developed withdrawal criteria during the study and was not withdrawn.
- Subject received wrong treatment or incorrect dose of study.
- Subject took prohibited concomitant medication.

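### SAP 4.0 narrows the protocol's any-dose Safety Analysis Set, so a dosed M19-130 non-completer or a subject given only unassigned drug would be left out (minor)

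*SAP*

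**What the plan says.** The two documents define the same set differently.

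- Protocol 7.2: "The Safety Analysis Set includes all subjects who received at least 1 dose of study drug in LTE Study M20-186".
- SAP 4.0: "The Safety Analysis Set also includes all subjects who completed Study M19-130 and received at least 1 dose of assigned study drug in Study M20-186".

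Both then group subjects by the treatment sequence they actually received. The SAP adds a rule for deciding it: "A subject's actual treatment will be determined by the most frequent dose regimen received".

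The set carries the main purpose of the study. SAP 2.1 says: "The primary objective is to evaluate the longer-term safety and tolerability of elsubrutinib and upadacitinib given alone or as the ABBV-599 (elsubrutinib/upadacitinib) combination". Protocol 7.4 says: "All safety analyses will be performed on the Safety Analysis Set". SAP 9.1 says: "Safety analyses will be carried out using the Safety Analysis Set". SAP 6.0 summarises study drug duration on the same set, and SAP 9.2.4 builds patient-years from study drug exposure.

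SAP Appendix A lists deviation categories that include "Subject entered into the study even though s/he did not satisfy entry criteria" and "Subject received wrong treatment or incorrect dose of study". SAP 13.0 describes version 2.0 as an alignment with the protocol after the M19-130 interim analysis and a move to M20-186 data only for duration and safety. It does not mention narrowing the safety population.

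**The concern.** A safety population normally contains everyone exposed, because a subject dosed in error was still exposed. The SAP's two extra conditions can remove exposed subjects from the analysis that answers the primary objective. A subject removed this way loses both numerator and denominator: the adverse events leave the summary tables, and the exposure leaves the patient-years. Appendix A would count the deviation but would not report what happened to the subject.

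The denominators could also disagree. SAP 5.0 counts subjects who took at least one dose without either condition, so that count could exceed the safety denominator with nothing in the SAP to explain the gap.

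**Working it through.** **Inputs**

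- Set definitions: protocol 7.2 and SAP 4.0, as quoted.
- Entry criteria: protocol 5.1. Completion of M19-130 on study drug is part of criterion 3, one of several.
- Late discovery of entry violations: protocol 5.5 foresees a violation noticed after study drug has started.
- Size: protocol 4.1 projects 65 subjects in each of five M19-130 groups. Protocol 7.7 and SAP 2.4 expect 60% to 80% to enrol, 195 to 260 subjects.

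**Step 1. Reproduce the plan's figure**

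5 × 65 = 325; 0.60 × 325 = 195; 0.80 × 325 = 260. The stated range is reproduced.

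**Step 2. Apply each definition to the possible deviations**

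| Subject dosed in M20-186 | Protocol 7.2 | SAP 4.0, read literally |
|---|---|---|
| (a) Had not completed M19-130 | In | Out |
| (b) Breached another entry criterion (for example TB, ECG or background therapy), completed M19-130, took assigned drug | In | In |
| (c) Completed M19-130, sometimes given the wrong drug or dose, at least one assigned dose | In | In, grouped by most frequent regimen |
| (d) Only ever given drug other than that assigned | In | Out |

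The definitions part company only at (a) and (d).

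**Step 3. Check the as-treated rule against the word *assigned***

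The most-frequent-regimen rule has work to do in case (c), where a subject with one assigned dose and many of another regimen is in the set and is regrouped. So the rule and the inclusion wording can operate together. They pull apart only in case (d), the clearest instance of treatment differing from assignment, which never reaches the grouping step. The rule gives no help with case (a).

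**Step 4. Size**

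The documents give no count or rate for (a) or (d). Assuming k such subjects, the share of all enrolled is k/260 to k/195:

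| Assumed k | of 260 | of 195 |
|---|---|---|
| 1 | 0.38% | 0.51% |
| 2 | 0.77% | 1.03% |
| 5 | 1.92% | 2.56% |

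k = 0 is also possible.

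**The case against.** The strongest case on the other side is that the conditions merely restate who can be in the study. Completion of M19-130 is an entry criterion throughout the protocol. Kits are assigned to each subject by interactive response technology (protocol 5.7), and drug is dispensed at seven visits from Week 48 to Week 96 (protocol Appendix D). To receive no assigned dose at all, a subject would need an error at every dispensing, or an error followed by early stopping. The study is descriptive, so no test depends on the set. This argument stands as regards likelihood, and it is why the point is minor. It does not defend the wording: if no dosed subject is meant to be excluded, the conditions do nothing useful, and a programmer will implement what is written.

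A second argument is that information is not wholly lost, and this largely stands. Such subjects would still be counted in disposition (SAP 5.0) and among deviations (Appendix A). The Data Monitoring Committee's safety review carries no stated restriction to this set (protocol 6.3, SAP 11.2). The listings in SAP 9.2.9 name no population, although SAP 9.1 may imply one. The loss is therefore in the summary tables and rates; a reader should not infer that these subjects' events would go unseen everywhere.

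A third argument is that Appendix A's categories are general. That is right: neither names non-completion of M19-130 or a complete absence of assigned drug, and most subjects counted there would remain in the Safety Analysis Set.

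**Conclusion.** The point holds in a narrow form. On its literal wording the SAP set is smaller than the protocol's, for no stated reason. It omits two kinds of exposed subject from the safety summaries and patient-years: the dosed non-completer of M19-130, and the subject who received only unassigned drug. The number is unknown, probably very small and possibly zero. One subject is about 0.4% to 0.5% of the anticipated total, taking the plan's 195 to 260 as the enrolment. Severity is minor.

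Three stronger inferences are not supported:

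- *That wrongly entered or wrongly dosed subjects in general are excluded.* Cases (b) and (c) stay in.
- *That SAP 4.0 flatly contradicts its own as-treated rule.* There is tension for case (d) only.
- *That the effect can be sized per treatment sequence, for example for the subjects moving from placebo.* This would need the 60% to 80% range to apply equally to every arm, a 1:1 placebo split and no discontinued group. The split is described only for the period before the M19-130 interim analysis (protocol 4.1). After it, protocol 5.8 gives no ratio, groups may be discontinued, and SAP 5.0 and 8.1 say the analysis groups may change.

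**What to change.** In SAP 4.0, define the Safety Analysis Set as in protocol 7.2: every subject with at least one dose of any study drug in M20-186, with no condition on M19-130 completion or on assignment. Keep the as-treated grouping by most frequent regimen. The SAP's FAS sentence carries the same two conditions and the protocol's does not, so align its inclusion wording with protocol 7.2 as well.

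The cost is one sentence for the safety set and a matching edit for the FAS. No new data are needed and study conduct does not change. As a check at reporting, the safety denominator should then equal the disposition count of subjects who took at least one dose.

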5.0 Subject Disposition

The total number of subjects who were enrolled and treated will be summarized.

A summary of subject accountability will be provided where the number of subjects in each of the following categories will be summarized for each treatment group:

- Subjects enrolled in the study;
- Subjects who took at least one dose of study drug;
- Subjects who completed protocol-specified treatment;
- Subjects who prematurely discontinued study drug (all reasons and primary reason).

For end of study participation, the number and percentage of subjects who completed the protocol defined follow-up period (or did not with associated reasons) will be summarized overall and by treatment group.

The treatment groups will be described as follows indicating treatments from Study M19-130 to extension Study M20-186:

- Group 1: Elsibrutinib 60 mg/upadacitinib 30 mg to elsbibrutinib 60 mg/upadacitinib 30 mg
- Group 2: Elsibrutinib 60 mg/upadacitinib 15 mg to elsbibrutinib 60 mg/upadacitinib 15 mg
- Group 3: Elsibrutinib 60 mg to elsbibrutinib 60 mg
- Group 4: Upadacitinib 30 mg to upadacitinib 30 mg
- Group 5a: Placebo to elsbibrutinib 60 mg/upadacitinib 30 mg
- Group 5b: Placebo to elsbibrutinib 60 mg/upadacitinib 15 mg

Treatment groups above are subject to change depending on potential M20-186 treatment re-assignments after M19-130 Interim Analysis.

6.0 Study Drug Duration and Compliance

Study Drug Duration

A summary of study drug duration (days) will be provided by each treatment arm for the Safety Analysis Set.

The duration of exposure to study drug will be summarized for each group as specified in Section 5.0, with the number of subjects, mean, standard deviation, median, minimum and maximum values. In addition, the number and percentage of subjects exposed to study drug will be summarized for Study M20-186 treatment period based on the following duration intervals:

- ≥ 1 day

- ≥ 57 days
- ≥ 113 days
- ≥ 169 days
- ≥ 225 days
- ≥ 281 days
- ≥ 337 days
- ≥ 393 days

The exposure to study drug in days for Study M20-186 period is calculated as:

Exposure = (date of last study medication in Study M20-186 – date of first study medication in Study M20-186 + 1)

Compliance

Study drug compliance will be summarized for each treatment group for FAS population. Descriptive statistics will be provided including sample size, mean, standard deviation, median, minimum and maximum.

Treatment compliance (TC) will be calculated using the following formula:

$$TC = \frac{\text{Total number of tablets/capsules taken}}{(last \ dose \ date - first \ dose \ date + 1) \times <\text{number of tablets/capsules per day}>} \times 100\%$$

- The total number of tablets/capsules taken will be calculated as the total number of tablets/capsules dispensed minus the total number of tablets/capsules returned.
Note: If the bottle is not returned, total number of tablets/capsules returned is assumed to be 0.
- In M20-186: number of tablets per day is 1 and number of capsules per day is 3.

7.0 Demographics, Baseline Characteristics, Medical History, and Prior/Concomitant Medications

Demographics, baseline or disease characteristics, medical history, and prior and concomitant medications will be summarized for the FAS overall and by treatment group as described in Section 5.0. Categorical variables will be summarized with the number and percentage of subjects; percentages will be calculated based on the number of non-missing observations. Continuous variables will be summarized with descriptive statistics (number of non-missing observations, mean and standard deviation, median, minimum and maximum).

7.1 Demographics and Baseline Characteristics

The following demographic and baseline characteristics, as measured at baseline of the Study M19-130 study, will be summarized.

Demographic Characteristics

- Sex (male, female)
- Age (years)
- Age category [18 – < 40 years old, 40 – < 65 years old, \geq 65 years old]
- Ethnicity (Hispanic or Latino, Not Hispanic or Latino)
- Race (White, Black or African American, American Indian or Alaska Native, Native Hawaiian or Other Pacific Islander, Asian, Other)
- Geographic region (North America, South/Central America, Western Europe, Eastern Europe, Asia Japan, Asia Other, Other)
- Weight (kg)
- Weight Categories (< 60 kg, \geq 60 kg)
- Height (cm)
- BMI (kg/m²)
- Body Mass Index (BMI) Category (kg/m²) (BMI < 25, BMI \geq 25)

Other Baseline Characteristics

The following continuous variables will be summarized:

- SLEDAI-2K score
- Patient's Global Assessment of Disease Activity score
- Physician's Global Assessment of Disease Activity score
- LupusQoL score
- SF-36 score
- Time since onset of lupus (years), which will be calculated as follows:
Time since onset of lupus (years) = year of first dose – year of initial diagnosis of SLE
- Number of tender joints (from 28-tender joint count)
- Number of swollen joints (from 28-swollen joint count)
- Daily dose of corticosteroid (mg/day)
- CLASI Total Activity Score
- CLASI Total Damage Score
- Complement C3 and C4 levels
- Anti-dsDNA level
- Urine protein to urine creatinine ratio
- Serum immunoglobulin (Ig)G and IgM concentrations
- Creatinine

The following categorical variables will be summarized:

- Anti-dsDNA status (positive defined as ≥ 30 IU/mL) (positive, negative)
- SLEDAI-2K status (< 10 , ≥ 10)
- British Isles Lupus Assessment Group (BILAG) organ system involvement at baseline (yes or no for each organ system domain). Involvement requires a baseline BILAG disease activity score of A or B.

- BILAG A organ system involvement at baseline (yes or no for each organ system domain).
- SLEDAI-2K organ system involvement at baseline (yes or no for each organ system domain).
- C3 status (less than the lower limit of normal [LLN] (< 90.0 mg/dL)
- C4 status (less than LLN [< 10.0 mg/dL])
- Anti-Smith antibodies (≥ 30 AU/mL) (yes, no)
- Corticosteroid use (yes or no), and within those taking corticosteroids, < 10 mg/day or ≥ 10 mg/day.
- Corticosteroid use (yes or no), and within those taking corticosteroids, < 7.5 mg/day or ≥ 7.5 mg/day.
- Immunosuppressant use (yes or no):
 - Mycophenolate use (yes or no)
 - Azathioprine use (yes or no)
 - Methotrexate use (yes or no)
 - Tacrolimus use (yes or no)
 - Cyclosporine use (yes or no)
 - Leflunomide use (yes or no)
- Antimalarial use (yes or no):
 - Hydroxychloroquine (yes or no)
 - Chloroquine (yes or no)
 - Quinacrine (yes or no)

Clinical Tests at Screening

- Chest x-ray
- Tuberculin PPD skin test, QuantiFERON TB Gold test
- Serum pregnancy test

Immunization History

- Herpes Zoster immunization
- Hepatitis B immunization

Tobacco/Nicotine and Alcohol Use

- Tobacco/Nicotine Use (current, former, never, or unknown)
- Alcohol Use (current, former, never, or unknown)

7.2 Medical History

Medical history data will be coded using the Medical Dictionary for Regulatory Activities (MedDRA). The actual version of the MedDRA coding dictionary will be noted in the statistical tables and clinical study report. Medical history data will be summarized and presented for the FAS population using body systems and conditions/diagnoses as captured on the CRF. The body systems will be presented in alphabetical order and the conditions/diagnoses will be presented in alphabetical order within each body system. The number and percentage of subjects with a condition/diagnosis will be summarized for each treatment group as well as overall. Subjects reporting more than one condition/diagnosis within a body system will be counted only once for that body system. No statistical comparison will be performed for medical history reporting.

7.3 Prior and Concomitant Medications

Prior and concomitant medications will be summarized by each treatment group as well as overall for the FAS.

Prior medications are those medications taken prior to the first dose of study drug in Study M19-130. This includes medications with a start date before the first study drug administration date, regardless of the end date of these medications. Medications taken on the day of the first dose of study drug are not counted as prior medications.

Concomitant medications are those medications, other than study drug, taken after the first dose of study drug in Study M20-186 and within 1 day of the last dose of study drug. This includes medications with a start date between first study drug administration in Study M20-186 and last study drug administration + 1 day, as well as, medications with a start date prior to first dose of study drug in Study M20-186 and which are ongoing after first dose of study drug. Medications taken on the day of the first dose of study drug in Study M20-186 are counted as concomitant medications.

The number and percentage of subjects who received a prior medication and the number and percentage of subjects who received a concomitant medication will be tabulated separately by the generic name assigned by the most current version of the World Health Organization (WHO) Drug Dictionary.

8.0 Efficacy Analyses

8.1 General Considerations

Analysis of efficacy endpoints will be conducted on the FAS based on treatment sequence as randomized for Study M19-130 and continued/reassigned to rollover into Study M20-186. For all efficacy endpoints, the descriptive statistics will be provided by treatment group. The statistics include number of observations, mean, standard deviation, minimum, median, and maximum for continuous variables; and number and percentage of subjects for categorical variables.

The analysis treatment groups will be described as follows indicating treatments from Study M19-130 to extension Study M20-186:

- Group 1: Elsubrutinib 60 mg/upadacitinib 30 mg to elsubrutinib 60 mg/upadacitinib 30 mg
- Group 2: Elsubrutinib 60 mg/upadacitinib 15 mg to elsubrutinib 60 mg/upadacitinib 15 mg
- Group 3: Elsubrutinib 60 mg to elsubrutinib 60 mg
- Group 4: Upadacitinib 30 mg to upadacitinib 30 mg

- Group 5a: Placebo to elsubrutinib 60 mg/upadacitinib 30 mg
- Group 5b: Placebo to elsubrutinib 60 mg/upadacitinib 15 mg

Analysis treatment groups above are subject to change depending on potential M20-186 treatment re-assignments after M19-130 Interim Analysis.

The Baseline for all efficacy analyses in this study will be the Baseline in Study M19-130, i.e., the last non-missing observation before the first administration of study drug in Study M19-130 or randomization in Study M19-130 if no study drug is given.

